Mexidol FORTE 250 is an inhibitor of free-radical processes, membrane protector with antihypoxic, stress-protective, nootropic, antiepileptic and anxiolytic action. The drug increases the body's resistance to various damaging factors in pathological conditions (hypoxia and ischaemia, impaired cerebral circulation, intoxication with ethanol and antipsychotic drugs). Anti-stressor effect is manifested in normalization of post-stress behaviour, somatovegetative disorders, restoration of sleep-wake cycles, disturbed learning and memory processes, reduction of dystrophic and morphological changes in various brain structures. It has hypolipidemic action, reduces the content of total cholesterol and low-density lipoproteins. Mexidol® FORTE 250 improves the functional state of ischaemic myocardium. It ensures the integrity of morphological structures and physiological functions of ischaemic myocardium. In conditions of coronary insufficiency it increases collateral blood supply of ischemic myocardium, promotes preservation of cardiomyocyte integrity and maintenance of their functional activity. It effectively restores myocardial contractility in reversible cardiac dysfunction. It stabilizes the membrane structures of blood cells (red blood cells and platelets), reducing the likelihood of haemolysis.

Clinical efficacy and safety

It improves metabolism and blood supply to the brain, improves microcirculation and rheological properties of blood, reduces platelet aggregation.

It improves the clinical course of myocardial infarction, increases the efficacy of therapy, and reduces the incidence of arrhythmias and intracardiac conduction disturbances [43]. It normalizes metabolic processes in ischemic myocardium, increases antianginal activity of nitrates, improves blood rheological properties, reduces the effects of reperfusion syndrome in acute coronary insufficiency.

Mexidol® FORTE 250 has a pronounced antitoxic effect in withdrawal syndrome. It

eliminates neurological and neurotoxic manifestations of acute alcohol intoxication, restores behavioural disorders, autonomic functions, and is also able to relieve cognitive impairment caused by long-term ethanol intake and its withdrawal.

It reduces enzymatic toxæmia and endogenous intoxication in acute pancreatitis.

Under the influence of the drug, the effect of tranquilising, neuroleptic, antidepressant, sleeping and anticonvulsant drugs is enhanced, which allows to reduce their doses and side effects.

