Oral administration of Mexidol® FORTE 250 film-coated tablets, 250 mg (RPC PHARMASOFT LLC, Russia) is carried out by patients based on the investigator's decision to transfer the patient to the next stage of therapy. The protocol regulates the possibility to start oral administration of the investigational product with the permission of the investigator only after completion of a full ten-day course of intravenous therapy with Mexidol® solution for intravenous and intramuscular administration, 50 mg/ml (RPC PHARMASOFT LLC, Russia).

On the basis of previously conducted clinical studies it is possible to conclude about possible efficacy and safety of sequential application of dosage forms and routes of administration of Mexidol® and Mexidol® FORTE 250, in the treatment of patients with ischaemic stroke, the total duration of use of different dosage forms of the investigational product (70 days) is aimed at reducing neurological symptoms both in the acute and acute periods of ischaemic stroke, and at early recovery of functions in the early recovery period.

The proposed placebo-controlled trial design, as well as blinding, will allow to evaluate the efficacy of sequential therapy with Mexidol® in patients with ischaemic stroke, providing the highest level of evidence for the trial of the trial, while minimising the majority of subjective factors on the part of both the patient and the physician.

Treatment of patients with ischaemic stroke based on evidence-based medicine includes the following items: general monitoring (control of blood pressure and temperature, glycaemia and blood ionic composition), specific treatment in the acute phase (intravenous or intra-arterial thrombolysis), preventive therapy (anticoagulants, antiplatelet drugs, surgery on carotid vessels). Currently, among the strategies that reliably improve the results of treatment and outcomes of acute stroke, the level of evidence A is: interventions aimed at maintaining the functioning of important organs and systems, earlier administration of acetylsalicylic acid, thrombolysis, hemicraniectomy, and treatment of the patient in a specialised stroke unit [Stroke: Manual for doctors / Edited by L.V. Stakhovskaya, S.V. Kotov. - M.: LLC "Medical Information Agency", 2013. - 400 p.: ill].

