6.5. Concomitant therapy

Patients will receive standard (baseline) therapy according to the Clinical Guidelines "Ischaemic Stroke and Transient Ischaemic Attack in Adults", 2015.

Baseline therapy includes correction of disorders of systemic and cerebral hemodynamics, rheological and coagulation properties of blood, prevention of complications of stroke. However, standard therapy drugs should not be classified as unauthorized in the present trial.

If concomitant pathology is not a criterion for exclusion of the patient from the trial, the treatment of concomitant pathology within the framework of this protocol is carried out according to the accepted standard scheme. Concomitant therapy drugs should not be classified as unapproved protocols.

Concomitant therapy (other than protocol prohibited drugs) for acute or chronic conditions may be continued as indicated. Information on concomitant medications (trade or international nonproprietary name, dose or dose modifications, indication, start date, discontinuation date) should be recorded in the eCRF.

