Interval (quantitative) data will be described using: arithmetic mean, standard deviation, median, lower (25%) and upper (75%) quartiles, minimum, maximum and coefficient of variation. Categorical (qualitative) data will be described using frequencies, percentages and/or fractions.

To compare quantitative data distributed according to the normal distribution law, it is planned to use standard parametric criteria: Student's t-test for dependent/independent samples, analysis of variance (ANOVA) for repeated measures.

It is planned to use standard nonparametric criteria to compare quantitative data distributed according to a law other than normal: Mann-Whitney U-test, Wilcoxon T-test, Friedman's criterion.

The test for conformity to the normal law of distribution will be carried out using the Shapiro-Wilk test.

Comparisons of frequencies of indicators between treatment groups will be made using Pearson's χ^2 test or Fisher's exact test.

9.7.3. Statistical methods for assessing the safety of using the investigational product and the comparator product

Safety parameters will be analysed in the ITT population.

Safety data will be analysed using the methods outlined for the application of the efficacy data assessment. Analyses of AEs will be performed based on an assessment of the incidence of adverse events / serious adverse events. Adverse events reported during the course of the trial will be presented by frequency (number of patients with AEs and number of such AEs in the group). AEs will also be presented by severity and relationship to investigational product

administration. Comparison of the number of patients with AE between therapy groups will be performed using Fisher's exact test or Pearson's χ^2 test.

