Table 16. Statistical analysis of physical examination parameters (outcome measure, template)

Investigational Product		Mexidol®				Placebo			
		Visit 0	Visit 2	Visit 3	Visit 4	Visit 0	Visit 2	Visit 3	Visit 4
Indicator 1									
Normal	Abs.								
	%								
Deviation	Abs.								
	%								
	%								
Comparison of groups (statistical criterion ¹⁸)									
p-level									
Indicator 2									
...									

Table 17. Distribution of patients by gender (template)

Gender		Mexidol®		Placebo	
Female	Abs.				
	%				
Male	Abs.				

¹⁷ Pearson's χ^2 criterion or Fisher's exact test

¹⁸ Pearson's χ^2 criterion or Fisher's exact test

Version 1.0 of 12.11.2021

Plan for statistical analysis of efficacy and safety parameters

	%	
Differences between	Pearson 's χ^2 criterion	
groups		

Table 18. Baseline patient characteristics (template)

Indicator ¹⁹	Mexitol®	Placebo
N		
Mean		
Median		
Min		
Max		
Qi		
Q3		
SD		
CV		
Comparison of groups	Statistical criterion ²⁰ , p-value	
Range diagram		Scatter diagram

Table 19. Total number of AEs (template)

AE	After administration of	
	Mexitol®	Placebo
Total number of AEs	Abs.	
Number of patients with detected AEs	Abs.	
	%	

Table 20. Relative risk of AEs (template)

Presence of adverse events in patients	Investigational Product	
	Mexitol®	Placebo
Identified	Abs.	
	%	
Not identified	Abs.	
	%	
Differences between preparations	Pearson 's χ^2 criterion or Fisher's exact test	
Relative risk of AEs [95% CI]		

¹⁹ Age, height, body weight or BMI

²⁰ T-test for independent samples or Mann-Whitney test depending on the type of distribution of the indicator

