**Plan for statistical analysis of efficacy and safety parameters**

	%		
Conditional.	Abs.		
	%		
Unclassifiable.	Abs.		
	%		
Inter-group differences	Pearson 's χ^2 criterion or Fisher's exact test		p-value

Table 24. Analysis of the distribution of AEs by foreseeability (template)

Expectancy	Investigational Product		
	Mexitol®	Placebo	
Expected	Abs.		
	%		
Unexpected	Abs.		
	%		
Inter-group differences	Pearson 's χ^2 criterion or Fisher's exact test		p-value

Table 25. Analysis of AR distribution (template)

AE	Investigational Product		
	Mexitol®	Placebo	
AR	Abs.		
	%		
Not an AR	Abs.		
	%		
Inter-group differences	Pearson 's χ^2 criterion or Fisher's exact test		p-value

Table 26. Analysis of the distribution of AEs by seriousness (template)

Seriousness	Investigational Product		
	Mexitol®	Placebo	
Serious	Abs.		
	%		
Nonserious	Abs.		
	%		
Inter-group differences	Pearson 's χ^2 criterion or Fisher's exact test		p-value

Table 27. Analysing the distribution of AEs by actions taken (template)

Version 1.0 of 12.11.2021

Protocol-Specific Version for Protocol #PHS-
APIS-004-MEX-SOL-TAV. version 1.3 dated
07.06.2021

CONFIDENTIAL

page 52 of 58

Plan for statistical analysis of efficacy and safety parameters

Actions taken	Investigational Product	
	Mexidol®	Placebo
No action was taken	Abs.	
	%	
Other (specific actions taken will be indicated)	Abs.	
	%	
Inter-group differences	Pearson 's χ^2 criterion or Fisher's exact test	p-value

Table 28. Analysis of the distribution of AEs by outcome (template)

Outcome	Investigational Product	
	Mexidol®	Placebo
Transition to SAE	Abs.	
	%	
Stabilization of the condition (no change in condition):	Abs.	
	%	
Recovery with consequences	Abs.	
	%	
Recovery/termination of an AE without consequences:	Abs.	
	%	
Improved condition	Abs.	
	%	
Unknown:	Abs.	
	%	
Inter-group differences	Pearson 's χ^2 criterion or Fisher's exact test	p-value

Plan for statistical analysis of efficacy and safety parameters

Table 29. Summary table of the incidence of reported AEs in the group taking Mexidol by severity with randomization numbers of patients (N=) (template)

AE/code, PT according to MedDRA version	Mild AE		Medium AE		Moderate AE		Life-threatening AE		Fatal AE		Total		Total
	R	UR	R	UR	R	UR	R	UR	R	UR	R	UR	R+UR

Table 30. Summary table of the incidence of reported AEs in the group taking placebo by severity with randomization numbers of patients (N=) (template)

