Adverse event/code, PT level according to MedDRA version	Mild AE		Medium AE		Moderate AE		Life-threatening AE		Fatal AE		Total		Total
	R	UR	R	UR	R	UR	R	UR	R	UR	R	UR	R+UR

Table 31. Summary table of the incidence of AEs after taking each Investigational Product (template)

Adverse event/code, PT level according to MedDRA version	Mexidol N=		Placebo N=		P-value (Statistical criterion)
	n	%	n	%	

Version 1.0 of 12.11.2021

Protocol-Specific Version for Protocol #PHS-APIS-004-MEX-SOL-TAV.
version 1.3 dated 07.06.2021

CONFIDENTIAL

page 54 of 58

Plan for statistical analysis of efficacy and safety parameters

Table 32. List of all adverse events for each patient (template)

Site number	Randomization number, full name	Demographic data	AE/code, PT according to MedDRA version	AE onset	Severity	Seriousness	Relationship	Actions taken in relation to the patient	Actions taken in relation to the investigational product	Concomitant therapy	Date the AE resolved	Outcome
		Age, years										
		gender										
		Weight, kg										
		Height, cm										
		race										

Table 33. MedDRA version classification of AEs (template)

Randomization number, initials	AE	MedDRA AE code, SOC level	MedDRA AE term, SOC level	MedDRA AE code, PT level	MedDRA AE term, PT level

Version 1.0 of 12.11.2021

Protocol-Specific Version for Protocol #PHS-APIS-004-MEX-SOL-TAV.
version 1.3 dated 07.06.2021

CONFIDENTIAL

page 55 of 58

Plan for statistical analysis of efficacy and safety parameters

Table 34. Summary table of the incidence of reported SAEs in the group taking Mexidol by severity with randomization numbers of patients (N=) (template)

Adverse event/code, PT level according to MedDRA version	Mild AE		Medium AE		Moderate AE		Life-threatening AE		Fatal AE		Total		Total
	R	UR	R	UR	R	UR	R	UR	R	UR	R	UR	R+UR

Table 35. Summary table of the incidence of reported SAEs in the placebo group by grade with randomization numbers of patients (N=) (template)

Adverse event/code, PT level according to MedDRA version	Mild AE		Medium AE		Moderate AE		Life-threatening AE		Fatal AE		Total		Total
	R	UR	R	UR	R	UR	R	UR	R	UR	R	UR	R+UR

Table 36. Summary table of the incidence of SAEs after taking each investigational product (template)

Version 1.0 of 12.11.2021

Protocol-Specific Version for Protocol #PHS-APIS-004-MEX-SOL-TAV.
version 1.3 dated 07.06.2021

CONFIDENTIAL

page 56 of 58

Plan for statistical analysis of efficacy and safety parameters

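### No planned adverse event comparison groups events by type, so a bleeding excess spread over several preferred terms would probably not show in any of them, although the protocol states an antiplatelet action

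*Protocol*

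**What the plan says.** **Pharmacology and background therapy.** Protocol section 2.2 states for both dosage forms that the product "improves microcirculation and rheological properties of blood, reduces platelet aggregation". Section 2.3.2 repeats the antiplatelet effect for hospital use in stroke. Under section 6.5 all patients receive baseline therapy that includes correcting "rheological and coagulation properties of blood, prevention of complications of stroke". Patients enter within 48 hours of an ischaemic stroke (section 5.1), and haemorrhagic infarction is a non-inclusion criterion (section 5.2).

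**Adverse event comparisons.** Protocol section 9.7.3 says: "Comparison of the number of patients with AE between therapy groups will be performed using" Fisher's exact or Pearson's chi-square test. The SAP table templates (section 13) then provide:
- any adverse event, yes or no, with a relative risk and 95% CI (Table 20, "Relative risk of AEs (template");
- pooled adverse events split by severity, relationship, foreseeability, adverse-reaction status, seriousness, action and outcome (Tables 21 to 28, for example "Analysis of the distribution of AEs by seriousness (template");
- one p-value per preferred term (Table 31, and Table 36 for serious events), with rows defined as "Adverse event/code, PT level according to MedDRA version".

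System organ class appears only in per-patient coding listings (Table 33, "MedDRA version classification of AEs (template", and Table 38), without an arm comparison. Neither document defines a bleeding group, a MedDRA query or an adverse event of special interest.

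**The concern.** An antiplatelet action on top of therapy that acts on coagulation makes bleeding a harm worth looking for. Bleeding events are coded to many preferred terms, such as epistaxis, haematuria, gastrointestinal haemorrhage and haemorrhagic transformation. Each term may be too rare to test alone, and together they are diluted in the any-event total. The plan has no level between these two.

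Little else would bring such an excess to light. Protocol Table 6.1 contains no coagulation test and Appendix 1 schedules no CT or MRI after Visit 0, so bleeding would surface mainly through adverse event reports. Objective 2 is to compare the frequency and severity of adverse events. A column of non-significant preferred-term rows could be read as reassurance that those tests cannot give.

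**Working it through.** **The plan's own figure.** The only sample size calculation is for the primary endpoint: 2 × (1.6449 + 0.8416)² × 0.802² / (0.292 − 0.027)² = 113.3, so 114 per group and 228 in total. Then 228 / 0.75 = 304 randomized. Both figures reproduce. With 1:1 allocation the ITT set used for safety has 304 / 2 = 152 per arm. The documents give no figure for detecting any adverse event.

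**Assumptions.** Bleeding rates are not in the documents, so a range is shown. Tests are two-sided Fisher at 0.05. Six preferred terms are taken as equally frequent and independent, with no multiplicity correction.

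**Formulas.**
- Power of one test = sum of Bin(a; 152, p_active) × Bin(b; 152, p_placebo) over all tables with a > b and Fisher p ≤ 0.05.
- Rate per term: p = 1 − (1 − P)^(1/6).
- Chance that at least one term is flagged = 1 − (1 − power per term)^6.
- Any-event rate = 1 − (1 − 0.213)(1 − P). The background is the earlier trial's 32 patients with an event out of 150 (21.3%, Protocol section 2.3.2).

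| Any bleeding, active v placebo | Rate per term | Power per term | Any of 6 terms | Any-event test | Grouped test |
|---|---|---|---|---|---|
| 12% v 4% | 2.11% v 0.68% | 4.3% | 23% | 20% | 68% |
| 9% v 3% | 1.56% v 0.51% | 1.6% | 9% | 12% | 51% |
| 6% v 2% | 1.03% v 0.34% | 0.3% | 2% | 7% | 31% |
| 8% v 4% | 1.38% v 0.68% | 0.7% | 4% | 7% | 23% |

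For the first row, 1 − (1 − 0.043)^6 = 0.23.

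**Sensitivity to the split.**
- At 12% v 4%, the chance that any term is flagged is 39% with four terms and 13% with eight.
- If four terms share the events 50/20/15/15, it is 42%.
- Dividing the rate by six (P/6) instead gives 20%, 8%, 2% and 4% for the four rows.

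**In counts.** A single term reaches p < 0.05 only at 6 v 0 (p = 0.030) or 8 v 1 (p = 0.036); 5 v 0 gives p = 0.060. Suppose 14 v 4 patients bleed. Grouped, p = 0.026. The risk difference is 14/152 − 4/152 = 9.2% − 2.6% = 6.6 percentage points, with standard error √(0.0921 × 0.9079/152 + 0.0263 × 0.9737/152) = 0.0268 and 95% CI 1.3 to 11.8 points. Split over six terms as 3 v 1, 3 v 1, 2 v 1, 2 v 1, 2 v 0 and 2 v 0, the p-values are 0.62, 0.62, 1.00, 1.00, 0.50 and 0.50.

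**The case against.** **The safety information does not point to bleeding.** The antiplatelet statement is one clause in a long list of actions. Neither side-effect list in section 2.2 contains a bleeding term, and the interaction text names no antithrombotic. The summary of the earlier placebo-controlled trial (150 patients, lower dose) describes no bleeding signal. This stands: a reader might infer that the drug is expected to cause bleeding, and the documents do not support that.

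**Section 2.5 is not a description of this trial's co-medication.** Its phrase "preventive therapy (anticoagulants, antiplatelet drugs, surgery on carotid vessels" belongs to an account of stroke care in general that also covers thrombolysis, and section 5.2 excludes patients who have had thrombolysis or thrombectomy. This stands too. The background-therapy point rests on section 6.5 alone.

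**The plan does compare more than totals and single terms.** Tables 21 to 28 carry p-values, haemoglobin, haematocrit and platelet counts are compared by arm (SAP Table 9), and Table 32 lists every event. So it would be too strong to say that an excess must be missed. But none of the adverse event tests isolates bleeding, and the laboratory comparisons are indirect.

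**Grouping is no cure.** At 6% v 4% the grouped test has only 7% power, and a non-significant grouped row could mislead in the same way. This stands, and it is why the estimate and interval should come before the p-value. Grouping was still more powerful than testing single terms at every rate tried.

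**It could be added later.** SAP section 10 allows methods to be supplemented. A term list chosen after unblinding would not, however, carry the weight of a pre-specified one.

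**Conclusion.** The gap is real and modest. No planned adverse event comparison lies, by type of event, between all events pooled and one preferred term, so a bleeding excess spread over several terms would probably not show. Over the four assumed scenarios, grouping raises the chance of detection from between 2% and 23% to between 23% and 68%. These figures rest on assumed rates, 152 per arm and six equal, independent terms. A dominant single term narrows the difference. Applying the Benjamini-Yekutieli correction of SAP section 9, whose scope is not stated, to the preferred-term rows would widen it.

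Two stronger readings are not supported. The documents give no evidence that the product causes bleeding. Nor would grouping make detection certain: it works only on reported events, and silent haemorrhagic transformation stays unrecorded without follow-up imaging.

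**What to change.** In SAP section 10, before unblinding:
- Fix one list of bleeding preferred terms, including symptomatic haemorrhagic transformation.
- Report patients with at least one such event per arm, n (%), with the risk difference and its 95% CI as the main result and Fisher's p-value as support.
- State that this comparison lies outside the Benjamini-Yekutieli correction.
- State that a non-significant result does not exclude a moderate excess, and that silent haemorrhagic transformation is not captured because no follow-up imaging is scheduled.

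The preferred-term tables can stay as they are. A system organ class table would not do the same job, because bleeding terms fall under several classes.

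The cost is one SAP paragraph and one table from data already coded, with no new procedure, visit or patient. The downside is one more comparison, with up to a 5% chance of a false flag.

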2.3. Results of preclinical and clinical studies

2.3.1. Results of preclinical studies

Pharmacokinetics

Studies have established that ethylmethylhydroxypyridine succinate has high bioavailability. When parenterally administered to rats, it was rapidly absorbed from the abdominal cavity with a half-absorption period of 0.94 hours; maximum concentrations in plasma were reached in 3 hours, and in the brain and liver of animals - in 2-3 hours [Voronina T.A., 2003].

In experiments conducted on mongrel rats, it was found that when administered orally, the elimination stage of the drug has a clear biphasic character [Miroshnichenko I.I. et al., 1994].

In the trial of pharmacokinetics and biotransformation of ethylmethylhydroxypyridine succinate in mice, the concentration of the drug was determined by high-performance liquid chromatography (HPLC) in blood plasma in the interval from 1 to 90 min; in urine - 24 h after administration of ethylmethylhydroxypyridine succinate [Kravtsova O.Yu., 2005].

In the trial of biotransformation features of ethylmethylhydroxypyridine succinate, 5 metabolites represented by dealkylated and conjugated transformation products were isolated and identified: (1) 2,6-dimethyl-3-oxypyridine; (2) 6-methyl-3-oxypyridine; (3) phosphate conjugate 2-ethyl,6-methyl-3-oxypyridine; (4) glucuron conjugate 2-ethyl-6-methyl-3-oxypyridine; (5) phosphate-glucuron conjugate 2-ethyl-6-methyl-3-oxypyridine. The first metabolite was found to have the same anxiolytic activity as the parent substance, and even surpasses it in antihypoxic and sedative effects. The third metabolite plays an important role in the membranotropic action and pharmacological activity of ethylmethylhydroxypyridine succinate, prolonging the effect of the original drug due to the formation of hepatic depot [Kravtsova O.Yu. et al., 2003].

Toxicity

Acute toxicity

Determination of acute toxicity of tablet form of Mexidol® preparation was carried out on two species of animals (mice, rats) at two routes of administration (intraperitoneally and orally). After administration of the drug, animal behaviour, appearance, reactions to external stimuli were observed for 14 days and in case of death, the number of deaths and clinical picture of death were noted. It was found that at intraperitoneal administration of Mexidol® in experiments on mice LD50 was 430 (310-602) mg/kg. When the drug was administered orally to mice, the LD50 was 2000 mg/kg. When Mexidol® was administered intraperitoneally to rats, the LD50 was 820 (700.8-959) mg/kg. When the drug was administered orally to rats LD50 was 3000 mg/kg [Seredenin S.B. et al., 1994].

The trial of acute toxicity of the injectable form of Mexidol® was carried out on mongrel rats during 14 days by intramuscular injections - in the thigh, and intravenous injections - in the tail vein. When administering the technically maximum possible volume (dose 2500 mg/kg, volume 10 ml), no lethal effects were observed [Kosmachev A.B., 2004].

The results of toxicometry, data of observations of experimental animals in the postintoxication period of acute poisoning, as well as necropsy data allow us to assign the drug Mexidol® to the following classes of toxicity: tablet form - class 4 (low toxicity), solution for IV and IM administration - class 5 (practically non-toxic drug substances). [Hodge H. et al., 1975].

Subacute toxicity

Subacute toxicity of the preparation Mexidol® solution for intravenous and intravenous administration was studied on 150 mongrel rats, of which 30 animals constituted the control

group for each route of administration. The drug was administered once daily for 14 days. Two administration techniques were investigated: intramuscularly (into the thigh muscle) and intravenously (into the tail vein). Two doses, 10 mg/kg and 500 mg/kg (50 times higher), were studied. After the end of administration, animals of all groups were slaughtered and sent for autopsy and pathomorphological examination. Pathomorphological trial showed that intramuscular and intravenous administration of the tested drug Mexidol® at doses of 10 mg/kg and 500 mg/kg does not cause pathological morphological changes in internal organs, including the brain and does not have an irritating effect at the injection sites [Kosmachev A.B., 2004].

Chronic toxicity

Experiments to trial the general toxic effect of the tablet form of Mexidol® were conducted on 48 mongrel white rats of both sexes. Rats were administered Mexidol® as a suspension of crushed tablets on distilled water per os (via a probe into the stomach) once a day for 6 months at the following dosages: 25 mg/kg (therapeutic dose) and 250 mg/kg, ten times the therapeutic dose. As a result of experiments it was found that the drug does not cause pathological changes in vital organs and systems of the animal body, even applied in a dose that is ten times higher than the therapeutic dose. At histological trial it was found that preparation Mexidol® does not cause pathological changes of internal organs, and also does not have local irritant effect [Seredenin S.B. et al., 1994].

Specific toxicity

As a result of the conducted studies it was found that Mexidol® when administered during pregnancy at a dose of 250 mg/kg intragastrically has no embryotoxic and teratogenic effect. When trialing allergic properties of the oral dosage form of Mexidol®, the data of reactions of general and active cutaneous anaphylaxis indicate the presence of sensitising properties when the drug is administered at a dose of 25 mg/kg, which can be considered as a manifestation of individual sensitivity, since the number of animals with positive reactions did not exceed 50%. The trial of mutagenic activity was carried out on mice. Testing has not revealed in the oral dosage form of Mexidol® mutagenic activity at any stage of the spermatogenesis cycle [Seredenin S.B. et al., 1994].

Pharmacological effects

The effect of Mexidol® on the process of Fe^{2+} -induced LPO of apo-B-containing serum lipoproteins was studied by recording chemiluminescence kinetics. Mexidol® in different concentrations was found to inhibit the LPO process of apo-B lipoproteins isolated from blood serum of healthy donors by precipitation method. The established mechanism of inhibition is due to the effect of the drug on the state of Fe^{2+} ions and/or the efficiency of their interaction with lipoproteins. The detected antioxidant effect of Mexidol® may be an important link in the general mechanism of its antioxidant action. [Tesankin Y.O., Davydov B.V., 2006].

The lipid spectrum in the brain tissue in different terms of post-resuscitation period with subcutaneous administration of Mexidol® at a dose of 50 mg/kg was studied in rats in the experiment when modelling clinical death by cardiovascular bundle constriction according to V.G. Korpachev. The administration of the drug increased the phosphatidylserine content, normalised the relative amounts of phosphatidylethanolamine and cholesterol, free fatty acids and the absence of lysophosphatidylserine in the remote post-resuscitation period. Mexidol® promoted the formation of protective-adaptive reactions at the level of lipid component of brain cell membranes in the early reperfusion period, preventing the development of irreversible damage to the phospholipid metabolism of the brain in the remote postreanimation period. [Andreeva N.N., Mukhina I.V., 2005].

The effect of Mexidol® and its structural components on carbohydrate content and lipid peroxidation in the liver of white mice under acute stress when administered at a dose of 100 mg/kg intraperitoneally was studied. Mexidol® inhibited the increase of glycogen content in liver tissue without affecting the content of free glucose in it. At the same time, the drug inhibited LPO processes. Protective effect of Mexidol® in the liver can be explained by its

membrane-stabilising effect, which is manifested by inhibition of membrane LPO and changes in their phospholipid composition, as well as normalization of the functioning of membrane-bound enzymes [Devyatina T.A. et al., 1999].

The trial of the use of Mexidol® on the model of intracerebral posttraumatic haematoma (haemorrhagic stroke) in rats showed its efficacy at a dose of 100 mg/kg when administered for 7 days. In the experiment the drug significantly reduced the frequency of neurological disorders (paresis, manoeuvres), increased the survival rate of animals. Mexidol® improved learning and memory processes in rats with haemorrhagic stroke (HS) in the test of conditioned passive avoidance reflex, influenced motor activity in the open field test. The author emphasised that a particularly important consequence of the drug's action is its ability to exert a complex effect on the different disorders occurring after HS. Mexidol® reduces the mortality of animals after stroke, improves neurological status, eliminates post-stroke memory disorders, has anxiolytic effect, improves orientation-research behaviour [Kraineva V.A., 2006].

Mexidol® prevented the development of amnesia in mice induced by complex extreme exposure, attenuating this type of amnesia in mice with bilateral ligation of the common carotid arteries. Mexidol® induced a pronounced anti-amnesic effect in models of amnesia induced by maximal electroshock, scopolamine and acute normobaric hypoxia with hypercapnia. Mexidol® at microelectrophoretic administration at a dose of 100 mg/kg depressed the spontaneous activity of neurons of different brain structures 4.2-7.4 times more often than stimulated. [Soloviev N.A., Yasnetsov V.V., 2006].

In another trial on the model of local cerebral ischaemia (LCI) of rabbits, an experimental evaluation of neuroprotective efficacy of Mexidol® at a dosage of 5 mg/kg intramuscularly was carried out with the trial of cerebral and skin microhemodynamics, lipid peroxidation (LPO), oxygen transport function and blood COS, O₂ mass transfer parameters in brain tissues. Administration of Mexidol® in the early post-ischaemic period in rabbits with LCI caused a decrease in primary and secondary LPO products with an increase in the activity of the enzymatic link of the antioxidant system, improving the supply of brain tissues with O₂, and enhancing the processes of cerebral and intradermal haemodynamics. The use of Mexidol leads to normalization or improvement of a number of homeostatic constants of the organism, changes in which play an important role in the structure of the pathogenesis of cerebral ischemia, which, according to the authors, can serve as a pathogenetic justification for its use in the complex neuroprotective pharmacotherapy of patients with cerebrovascular pathology of ischemic genesis. [Nechipurenko N.I. et al., 2006].

The neuroprotective activity of Mexidol® during gravitational overload in craniocaudal position was studied on the model of total brain ischaemia in rats. It was found that intraperitoneal administration of Mexidol® at doses of 5, 10 and 100 mg/kg increased the survival rate of laboratory animals in hypergravity. The effectiveness of prophylactic use of this drug is due to the limitation of hyperglycaemia and lactate acidosis, LPO processes in the brain and in erythrocytes, reducing the permeability of erythrocyte membranes for calcium ions, maintaining the autoregulation reaction of cerebral vessels. [Makarova L.M., 2006].

Mexidol® in the experiment at a dose of 20 mg/kg at intraperitoneal administration had a favourable effect on blood supply of the myocardial ischemia zone after coronary occlusion in rats. The drug reduced the decrease in left ventricular pressure and velocity characteristics of contraction of the left ventricle of the heart with local ischaemia, as well as in the acute period of myocardial infarction led to a decrease in lactacidaemia, glucose extraction and reduction of the electronegative shift of the redox potential of the system lactate/pyruvate [Gatsura V.V., 1996].

